1.0 INTRODUCTION

The SPIRIT 48mm study is a prospective, single arm, open-label, multi-center global (US and outside of US) clinical investigation to evaluate the safety and effectiveness of the ABT Next Generation Drug Eluting Stent 48 mm everolimus-eluting coronary stent system (EECSS) (called “ABT NG DES 48” hereafter) in up to 107 subjects at up to 33 sites globally. The clinical outcomes from the SPIRIT 48 study will be compared to a performance goal (PG) established using historical control data from the SPIRIT Prime Long Lesion Registry (NCT00916370)^a. This clinical investigation will be conducted under an investigational device exemption (IDE) and is intended to support market approval of the ABT NG DES 48 in the United States.

This SPIRIT 48 study will be conducted in accordance with this CIP. All investigators involved in the conduct of the clinical investigation will be qualified by education, training, or experience to perform their tasks and this training will be documented appropriately.

1.1 Background and Rationale

Advances in coronary drug-eluting stent (DES) technology have improved the clinical outcomes associated with the treatment of complex coronary artery lesions, including long lesions. However, the currently available DES stent lengths in U.S. (maximum 40 mm)^b are inadequate to provide complete single stent coverage of long coronary artery lesions. Globally, commercial availability of stents with 48mm length are limited in certain geographic regions, leaving physicians in these regions with the limited option of overlapping stents for long coronary lesion treatment. It was reported by Raper *et. al.* that metal stent overlap in certain situations is associated with stent fracture, malposition, restenosis and delayed vascular healing, and increases the clinical event rates¹. In addition, Hoffmann *et. al.* reported that the use of multiple stents can also lead to increased procedure time, fluoroscopy time, contrast usage and cost, which have negative impacts on both patients and health economics². Thus, Abbott identified a need for a longer stent length.

The ABT NG DES 48 is a new iteration of the XIENCE family of stents, which includes XIENCE V[®], XIENCE PRIME[®], XIENCE XPEDITION[®], XIENCE ALPINE, XIENCE Sierra, and ABT NG DES 48. Over 13 million XIENCE family of stents have been implanted into patients with coronary artery disease (CAD)³. The XIENCE family of stents has been the subject of extensive clinical studies for the treatment of patients with CAD. There was a robust clinical program of Abbott-sponsored clinical investigations assesses the safety and effectiveness of the XIENCE family of stents, which encompasses over 40,000 patients across multiple geographies³. Overall, the safety and effectiveness of the XIENCE family of stents have been well established. As an iteration of the XIENCE family of stents, the ABT NG DES 48 is expected to be safe and effective in the treatment of coronary artery long lesions.

^a <https://clinicaltrials.gov/ct2/show/NCT00916370>

^b http://www.translumina.de/products7/TRL136_Yukon_Choice_PC_brochure_WTK_online_LR.pdf

Clinical Investigation Plan

2.0 CLINICAL INVESTIGATION OVERVIEW

2.1 Objective of the Clinical Investigation

The objective of the SPIRIT 48 study is to evaluate the safety and effectiveness of the ABT NG DES 48 in improving coronary artery luminal diameter in subjects with coronary artery disease (CAD) due to *de novo* native coronary artery long lesions.

2.2 Device(s) To Be Used in the Clinical Investigation

2.2.1 Name of the Device(s) Under Investigation

The study device for the SPIRIT 48 study is the ABT NG DES 48, an investigational device, with the following available sizes:

Table 2.2.1-1 ABT NG DES 48 Size Matrix

Stent Design	Product Diameter (mm)	48mm
Small	2.5	X
	2.75	X
	3.0	X
Medium	3.5	X
	4.0	X

The ABT NG DES 48 is manufactured by Abbott.

2.2.2 Intended Indication for Use

The ABT NG DES 48 is intended to be indicated for improving coronary artery luminal diameter in patients, including those with diabetes mellitus, with symptomatic heart disease due to *de novo* native coronary artery lesions (length \leq 44 mm) with reference vessel diameters of \geq 2.5 mm to \leq 4.25 mm. In addition, the ABT NG DES 48 is also intended to be indicated for treating *de novo* chronic total coronary occlusions.

2.2.3 Description of the ABT NG DES 48 Stent System

ABT NG DES 48 is a balloon-expandable stent made of L-605 Cobalt Chromium (CoCr) with a poly (n-butyl methacrylate) (PBMA) and copolymer of vinylidene fluoride and hexafluoropropylene (PVDF-HFP)/everolimus coating. The stent includes two designs – small and medium. The small and medium stent design patterns of ABT NG DES 48 are identical to the respective small and medium stent designs for XIENCE Sierra Everolimus Eluting Coronary Stent System (XIENCE Sierra), and are similar to the rest of the XIENCE family of stents and MULTI-LINK VISION and MULTI-LINK 8, which are the bare-metal stents on which the XIENCE family of stents is based. ABT NG DES 48 medium stent size, (stent diameters 3.50 – 4.00 mm), will have an increased post dilatation expansion diameter up to 5.75 mm, compared to 5.50 mm for XIENCE Sierra. There is no change to the post dilatation expansion diameter for the small stent design.

Clinical Investigation Plan

The ABT NG DES 48 stent systems are device/drug combination products consisting of a drug-coated stent and a balloon expandable delivery system. The stent is coated with a formulation containing everolimus, the active ingredient, embedded in a non-erodible polymer, which is identical to the FDA approved XIENCE Sierra, XIENCE Alpine, XIENCE Xpedition, XIENCE PRIME and XIENCE V EECSS.

2.2.3.1 Stent Platform

Stent platform is fabricated from a single piece of medical grade L-605 Cobalt Chromium alloy. The balloon expandable stent consists of serpentine rings connected by links similar in design to the MULTI-LINK VISION Coronary Stent family and the XIENCE Sierra stent.

2.2.3.2 Anti-proliferative Drug: Everolimus

The active pharmaceutical ingredient in the ABT NG DES 48 is everolimus. Everolimus [40-O-(2-hydroxyethyl)-rapamycin], a drug provided to Abbott by Novartis Pharmaceuticals Corporation, is a novel semisynthetic macrolide immunosuppressant, obtained through chemical modification of rapamycin. Everolimus is a drug that has been evaluated in clinical investigations in the US and Europe for use in conjunction with other medications to prevent heart and renal transplant rejection. The oral form of everolimus (Certican[®]) had received market approval in over 65 countries. Everolimus has been approved in the United States as Afinitor and is indicated for patients with advanced renal cell carcinoma and manufactured by Novartis Pharmaceuticals Corporation. The nominal drug dose density of 100 µg/cm² is ABT NG DES 48, which is identical to all the other predecessors of the XIENCE family of stents.

2.2.3.3 The ABT NG DES 48 Polymer Coating

The coating of ABT NG DES 48 is identical in composition and drug to polymer ratio as the XIENCE Sierra stent coating. The primer layer is composed of poly (n-butyl methacrylate) (PBMA). The drug matrix layer is a co-polymer of vinylidene fluoride and hexafluoropropylene (PVDF-HFP), which controls the release of the drug. PVDF-HFP is blended with the anti-proliferative drug everolimus.

2.2.3.4 ABT NG DES 48 Stent Delivery System

The ABT NG DES 48 stent delivery catheter is available in a rapid-exchange (RX) design with the balloon and stent at the distal end of the catheter. The proximal lumen provides for inflation of the balloon with contrast medium and the central distal lumen permits a guidewire to facilitate advancement of the catheter. The distal and intermediate portions of the device, the tip, and tapers of the balloon are coated with HYDROCOAT™ hydrophilic coating.

Radiopaque markers are positioned on the inner member underneath the balloon to provide accurate positioning of the stent/balloon in the artery. The balloon is designed to deliver an expandable stent of known diameter and length at specified pressures. Markers located on the outside of the proximal shaft help the physician gauge the delivery catheter position relative to the guiding catheter tip. An adaption arm on the proximal end of the device provides access to the inflation lumen. It is designed with a Luer-lock fitting to facilitate connection to an inflation device. There are no novel features of this device.

Clinical Investigation Plan

3.0 CLINICAL INVESTIGATION DESIGN

The SPIRIT 48 study is a prospective, single-arm, open-label, multi-center clinical investigation in up to 107 subjects at up to 33 global sites to evaluate the safety and effectiveness of the ABT NG DES 48 in the treatment of *de novo* native coronary artery long lesions.

3.1 Clinical Investigation Procedures and Follow-up Schedule

A total of up to 107 subjects will be registered in the SPIRIT 48 study. Subjects registered in the study must have exactly one single *de novo* native coronary target lesion (defined in **Section 5.3**), which is eligible to be treated by a single ABT NG DES 48. Planned overlap is not allowed for the treatment of target lesion. If a bailout stent is necessary for the target lesion, a XIENCE family stent with appropriate size (including the ABT NG DES 48) must be used. A non-target lesion, if is located in a different epicardial coronary vessel than the target lesion, is allowed to be treated by stents other than the ABT NG DES 48 per site's standard of care during index procedure. All subjects must be treated with only one ABT NG DES 48.

- Lesions and stent usage: up to two treated lesions, must have exactly one long lesion that is treated by one ABT NG DES 48
 - Single lesion: one *de novo* native coronary artery long lesion (> 32 mm and ≤ 44 mm) as the target lesion, that must be treated a single ABT NG DES 48
 - Two lesions: one target lesion and one non-target lesion, each in different epicardial coronary vessels:
 - Target Lesion: one *de novo* native coronary artery long lesion (> 32 mm and ≤ 44 mm), that must be treated with a single ABT NG DES 48
 - Non-target lesion: one *de novo* native coronary artery lesion, that must be treated by stents other than the ABT NG DES 48 per site's standard of care

A maximum of 40% of subjects with two treated lesions can be registered in the study. At least 50% of the subjects will be registered at US sites.

Each subject will be followed for a two-year period. All subjects will have a hospital or office follow-up visit at 30 days, 6 months, 1 year and 2 years. An office visit is required for 1-year follow-up. All follow-ups must be conducted directly with the subject. Refer to detailed follow-up schedule in **Section 6.5.4**.

Note: If the scheduled visit occurs outside of the allowed window, it is not considered a missed visit/contact. It is a protocol deviation but still considered a completed visit.

3.2 Measures Taken to Avoid and Minimize Bias

A Clinical Event Committee (CEC) and an angiographic core laboratory will be utilized in this study to minimize bias.

3.2.1 Clinical Event Committee

A Clinical Event Committee (CEC) will review and adjudicate all clinical endpoint events. The CEC will, as appropriate, determine if the event that occurred, was clinically indicated vs. non-clinically indicated, if

Clinical Investigation Plan

the cause of the event was cardiac or non-cardiac related or if the event was related to the investigational device, the ABT NG DES 48 or not. The CEC will also adjudicate the coronavirus disease 2019 (COVID-19) relatedness of a clinical endpoint event.

3.2.2 Angiographic Core lab

All angiographic data of this clinical investigation will be assessed by the Angiographic Core Lab. The Angiographic Core Lab will determine the type of revascularization (i.e., TLR, TVR or non-TVR), stent thrombosis, or necessary assessments. Angiography must be performed per the angiographic core laboratory guidelines. Angiographic data includes:

- Pre-procedure Morphology
- Pre-procedure quantitative coronary angiography (QCA)
- Post-procedure (Final) Morphology
- Post-procedure (Final) QCA
- Unscheduled visit Morphology and/or QCA

3.3 Suspension or Early Termination of the Clinical Investigation

While no formal statistical rule for early termination of the clinical investigation for insufficient effectiveness of the device under investigation is defined, the Sponsor reserves the right to discontinue the clinical investigation at any stage or reduce the follow-up period with suitable written notice to the investigator. Possible reason(s) may include, but are not limited to:

- Unanticipated adverse device effect (e.g., UADE) occurs and it presents an unreasonable risk to the participating subjects
- An oversight committee (e.g., Steering/Executive Committee, Data Monitoring Committee) makes a recommendation to stop or terminate the clinical investigation (such as higher frequency of anticipated adverse device effects)

Should the clinical investigation be discontinued by the Sponsor, subjects will be followed per routine hospital practice with device-related AEs reported to the Sponsor as per vigilance/commercial reporting requirements. The investigator shall return all clinical investigation materials (including devices) to the Sponsor, and provide a written statement to the IRB/EC (if applicable). All applicable clinical investigation documents shall be subject to the same retention policy as detailed in **Section 11.5** of the CIP.

A Principal Investigator, IRB/EC or regulatory authority may suspend or prematurely terminate participation in the clinical investigation at the investigational site(s) for which they are responsible. The investigators will follow the requirements specified in the Clinical Investigation Agreement.

If the Sponsor suspends or prematurely terminates the clinical investigation at an individual site in the interest of safety, the Sponsor will inform all other Principal Investigators.

If suspension or premature termination occurs, the Sponsor will remain responsible for providing resources to fulfill the obligations from the CIP and existing agreements for following the subjects

Clinical Investigation Plan

enrolled in the clinical investigation, and the Principal Investigator or authorized designee will promptly inform the enrolled subjects at his/her site, if appropriate.

4.0 ENDPOINTS

4.1 Primary Endpoint and Rationale

The Primary Endpoint of the SPIRIT 48 Study is target lesion failure (TLF) defined as a composite of cardiac death, target vessel myocardial infarction [TV-MI] (MI is per Society for Cardiovascular Angiography and Interventions (SCAI) definition⁴), and clinically indicated target lesion revascularization [CI-TLR]^c at 1 year. The 1-year TLF will be compared to a pre-specified performance goal (PG) of 20%. More details will be found in **Section 8** for the statistical analysis plan.

TLF is chosen as the primary endpoint because TLF is a standard endpoint that was proposed by ARC⁵ and is also recommended in FDA's draft guidance for coronary DES clinical trials⁶.

4.2 Secondary Endpoint(s)^d

- TLF in hospital, at 30 days, 180 days, and 2 years

Secondary endpoints are descriptive without a pre-specified statistical assumption.

4.3 Other Endpoint(s)^d

Other endpoints are descriptive and include:

- Acute Success: (combined clinical and angiographic)
 - Device Success (Lesion basis)
 - Procedural Success (Subject basis)
- Clinical Endpoint in hospital and at each clinical follow-up time point (30 days, 180 days, 1 and 2 years)
 - Composite:
 - All death, all MI and all revascularization (DMR)
 - Cardiac Death/MI
 - Individual:
 - Any death
 - Cardiac
 - Vascular
 - Non-cardiovascular

^c The first adjudicated COVID-19 likely related component of the primary endpoint event along with the subsequent follow-up data will be censored and will not contribute towards the primary endpoint analysis.

^d MI is per SCAI definition.

Clinical Investigation Plan

- All MI
 - Q-wave MI (QMI)
 - Non-Q-wave MI (NQMI)
- TV-MI
 - Type
 - QMI
 - NQMI
- Any Revascularization
 - All TVR (including TLR)
 - ID-TVR
 - All TLR
 - ID-TLR
 - All Non-TVR
- Stent thrombosis (per ARC definition)
 - Type
 - Definite
 - Probable
 - Possible
 - Time
 - Acute (≤ 1 day)
 - Subacute (>1 day ≤ 30 days)
 - Late (>30 days ≤ 365 days)
 - Very late (>365 days)

A secondary analysis with MI per ARC 2 definition⁷ and 4th universal definition⁸ will be performed for all endpoints containing MI. will be performed for all endpoints containing MI.

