1.4.2 Secondary Endpoints^b

The secondary endpoints for this study are target lesion failure (TLF) at each following clinical follow-up time point:

- In hospital
- 30 days
- 180 days
- 2 years

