1.4.3 Other Endpoints^b

- Acute Success (combined clinical and angiographic)
 - Device Success (Lesion basis)
 - Procedural Success (Subject basis)
- Clinical Endpoint in hospital and at each clinical follow-up time point (30 days, 180 days, 1 and 2 years)

Composite:

- All death, all MI and all revascularization (DMR)
- Cardiac death/MI

Individual:

- Any death
 - Cardiac
 - Vascular
 - Non-cardiovascular

^a The first adjudicated COVID-19 I kely related component of the primary endpoint event along with the subsequent follow-up data will be censored and will not contribute towards the primary endpoint analysis.

^b MI is per SCAI definition.

Statistical Analysis Plan

- All MI
 - Q-wave MI (QMI)
 - Non-Q-wave MI (NQMI)
- TV- MI
 - Type
 - QMI
 - NQMI
- Any Revascularization
 - All TVR (including TLR)
 - ID–TVR
 - All TLR
 - ID–TLR
 - All Non-TVR
- Stent thrombosis (per ARC definition)
 - Type
 - Definite
 - Probable
 - Possible
 - Time
 - Acute (≤ 1 day)
 - Subacute (> 1 day ≤ 30 days)
 - Late (> 30 days ≤ 365 days)
 - Very late (> 365 days)

A secondary analysis with MI per ARC 2 definition ^[2] and 4th universal definition ^[3] will be performed for all the endpoints containing MI.

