2.3.1 Primary Endpoint

The primary endpoint for this study is target lesion failure (TLF), defined as a composite of cardiac death, target vessel myocardial infarction [TV-MI] (MI is per Society for Cardiovascular Angiography and Interventions (SCAI) definition^[1]), and clinically indicated target lesion revascularization [CI-TLR] at 1 year. The 1-year TLF will be compared to a pre-specified performance goal of 20%.

The null (H_0) and alternative (H_A) hypotheses are stated as:

$$H_0: P_D \geq 20\%$$

$$H_A: P_D < 20\%$$

Where P_D represents the target lesion failure (TLF) rate at 1 year. The primary endpoint will be performed on the FAS population.

[REDACTED] The primary endpoint will be considered met if the null hypothesis is rejected at the one-sided 5% significance level.

Descriptive summary of TLF at different follow-ups may be displayed for the FAS and PP population.

[REDACTED]

Statistical Analysis Plan

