2.13 Sensitivity Analysis

The following sensitivity analyses of the primary endpoint will be carried out:

- The primary endpoint will be performed for the per-protocol (PP) population as a sensitivity analysis.
- Tipping point analysis will be conducted as a sensitivity analysis to evaluate the impact of the missing data for the primary endpoint.

[REDACTED]

[REDACTED]

Statistical Analysis Plan

- COVID-19 Related Events: [REDACTED]
- The exact test based on the binomial distribution will be conducted to test the primary endpoint [REDACTED]

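### Does the COVID-19 censoring rule leave it unclear which TLF figures are censored and which count all events?

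*Protocol*

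**What the plan says.** Protocol 4.1 defines the primary endpoint as TLF at 1 year: cardiac death, target-vessel MI (TV-MI) or clinically indicated target lesion revascularization. Footnote c is attached to it: "The first adjudicated COVID-19 likely related component of the primary endpoint event along with the subsequent follow-up data will be censored". SAP 1.4.1 attaches the same rule as footnote a, which ends by giving its scope: "along with the subsequent follow-up data will be censored and will not contribute towards the primary endpoint analysis". The footnote mark appears again at Protocol 8.2.1 and in the primary endpoint entry of Protocol Appendix X.

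The secondary endpoints in Protocol 4.2 are "TLF in hospital, at 30 days, 180 days, and 2 years", and SAP 1.4.2 matches. The other endpoints (Protocol 4.3, SAP 1.4.3) include cardiac death and TV-MI at 1 year. Both groups carry a different footnote, which gives only the MI definition.

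SAP 2.3.1 adds: "Descriptive summary of TLF at different follow-ups may be displayed for the FAS and PP population". SAP 2.13 lists "COVID-19 Related Events" among the sensitivity analyses of the primary endpoint, with the content blacked out. Protocol 3.2.1 supplies the data for either basis: "The CEC will also adjudicate the coronavirus disease 2019 (COVID-19) relatedness of a clinical endpoint event".

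**The concern.** The rule ends a subject's contribution to the primary analysis at the first COVID-19 likely related component. Nothing visible applies it to TLF at 30 days, 180 days or 2 years, or to 1-year cardiac death and TV-MI, and the visible Kaplan-Meier rule in SAP 2.2.3 has no COVID-19 provision. Those figures therefore read as counting all events. The TLF summary allowed in SAP 2.3.1 does not say on which basis its 1-year row stands.

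A cumulative rate cannot fall over time, and a composite cannot be rarer than one of its components, as long as one basis is used throughout. With two bases both can seem to happen, and a reader might suspect a data error or take the censored rate for the all-events rate. There is a second worry: a survivor's later TLF unrelated to COVID-19 is lost, which relies on non-informative censoring. At stake would be a misread 1-year TLF rate in a single-arm trial judged against a 20% performance goal.

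**Working it through.** **Inputs.** From Protocol 8.3 and SAP 2.4: N = 107, true 1-year TLF 10%, performance goal 20%, one-sided alpha 0.05, attrition 5%, stated power about 93%. The documents give no COVID-19 event rate. Assumed here: a share q = 1% or 2% of subjects has a non-fatal COVID-19 likely related component, in addition to the 10%, with a later TLF hazard h = 1 to 5 times the average.

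**The plan's own figure.** The test method is redacted. A Kaplan-Meier estimate with a plain Greenwood standard error, uniform attrition and half of the events peri-procedural gives 93.3% power in 20,000 simulated trials, against the stated 93%. This figure does not depend on how the other TLF rates are labelled.

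**The two bases side by side.**

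| Figure | Footnote carried | Basis on the visible text |
|---|---|---|
| Primary TLF at 1 year (Protocol 4.1, 8.2.1, Appendix X; SAP 1.4.1) | COVID-19 rule | Censored |
| TLF in hospital, 30 days, 180 days, 2 years (Protocol 4.2; SAP 1.4.2) | MI definition only | All events |
| Cardiac death and TV-MI at 1 year (Protocol 4.3; SAP 1.4.3) | MI definition only | All events |
| Per-protocol, tipping-point, exact-test and subgroup analyses of the primary endpoint (SAP 2.8, 2.13) | Rule comes with the endpoint | Censored |

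**What the anomaly would look like** (invented counts).
- Four TV-MIs at 1 year, one of them COVID-19 likely, and no other component: TV-MI 4/107 = 3.7%, primary TLF about 3/107 = 2.8%.
- Twelve TLFs by 180 days, two of them COVID-19 likely, and one more by 1 year: all-events 180-day TLF 12/107 = 11.2%; primary 1-year TLF, dropping the two subjects, about 11/105 = 10.5%; all-events 1-year TLF 13/107 = 12.1%.

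Both patterns follow directly from the footnote.

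**How often.** The chance of at least one such component is 1 - 0.99^107 = 0.659 for q = 1% and 1 - 0.98^107 = 0.885 for q = 2%. In simulations of 40,000 trials per setting, the 180-day all-events count exceeds the censored 1-year count in 0.6% of trials (q = 1%) and 2.2% (q = 2%) under a constant hazard. If half of TLF falls by day 30, the figures are 3.6% and 9.9%.

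**Later events lost.** With L = -ln 0.9 = 0.10536 and the COVID-19 component uniform over the year, P(later TLF) = 1 - (1 - exp(-hL))/(hL). This is 0.051, 0.098 and 0.223 for h = 1, 2 and 5. Multiplied by 107q, the expected loss is 0.05, 0.11 and 0.24 events for q = 1%, and 0.11, 0.21 and 0.48 for q = 2%. The simulated 1-year Kaplan-Meier rate is understated by at most 10.34% - 10.01% = 0.33 points, up to rounding. Pass/fail differs from an analysis that keeps survivors at risk in 0.7% to 1.3% of trials (q = 1%) and 1.3% to 2.5% (q = 2%).

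**Rule against all events.** The all-events 1-year rate is 1 - 0.90 x 0.99 = 10.9% (q = 1%) or 1 - 0.90 x 0.98 = 11.8% (q = 2%), against 10.0% under the rule. Pass/fail would differ in 5.1% to 5.4% and 12.5% to 12.9% of trials. This is the effect of the rule itself, not of any missing label.

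**The case for a change.** The strongest case for the concern is that the rule can matter. By the exact test, 15 events in 102 evaluable subjects gives p = 0.110; with two of them censored, 13 in 100 gives p = 0.047. A reader who takes the censored rate for the all-events rate could be misled, and one sentence in the SAP would prevent that at almost no cost. It is also true that no visible sentence states the all-events basis for the secondary and component figures. That basis is inferred from the scope of the footnote, and the SAP 2.3.1 summary sentence is silent on it.

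The inference stands as fair, and a clear note under each table would be good reporting practice. The rest does not make a defect. The pass/fail figures compare the prespecified rule with another estimand. The rule is the same in both documents, is fixed in advance and depends on independent adjudication, and the concern itself does not dispute it. An all-events companion estimate cannot be called absent when a COVID-19 sensitivity analysis of the primary endpoint is listed and only its content is hidden. Text around the SAP 2.3.1 summary sentence and the whole of SAP 2.2.4 are also blacked out, and what is redacted is not missing from the plan. A further estimate that keeps survivors at risk would recover less than half an event per trial even in the least favourable setting examined.

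**Conclusion.** The concern does not hold. The plan states the COVID-19 rule, limits it to the primary endpoint analysis, marks it wherever the endpoint lists define that endpoint, and gives the secondary and other endpoints a different footnote. Someone who finds primary TLF below TV-MI, or below 180-day TLF, has the explanation in the endpoint definition. SAP 2.11 confines formal testing to the primary endpoint in the full analysis set, so no second basis enters the decision; hypothesis, alpha, sample size and power are untouched.

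The sizes depend on an assumed COVID-19 component rate of 1% or 2% and an assumed Kaplan-Meier/Greenwood test. Under these assumptions the apparent fall from 180 days to 1 year occurs in about 0.6% to 10% of trials, and later events lost number at most 0.48 per trial. The true rate could be lower: only the likely related category triggers the rule (Protocol Appendix II), and recent COVID-19 is an exclusion (general exclusion criterion 27). Even at 1%, 34% of trials would have no such event, and the two bases would then agree exactly. Stating the basis under each table belongs to the table shells and the final report.
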